This MCT is needed to further quantify and expand upon our site's early data comparing hypothermic and standard ROTEM assay results. To date, no trials evaluating in-vivo hypothermic TEG or ROTEM assays exist in hypothermic trauma patients. Our aim is to fill the knowledge gap pertaining to the clinical impact of hypothermic testing, further identify and quantify blood product administration using hypothermic guided resuscitation practices, and ultimately compare hypothermic to standard protocols in a randomized controlled trial with intent to amend transfusion guidelines as indicated. Implementation and completion of this prospective multi-center trial is the first step towards these goals.

Determine if hypothermic testing protocols for ROTEM are associated with clinically significant differences in coagulation parameters compared to standard warm protocol testing. Our primary hypothesis is that results from hypothermic ROTEM assays will reflect more significant coagulopathy when compared to warmed samples. Our objective is to determine if hypothermic ROTEM samples will indicate a need for more plasma, cryoprecipitate and/or platelets for coagulopathy reversal compared to warmed samples.

Primary aim

To test the primary hypothesis, hypothermic ROTEMs parameters will be compared against standard warmed ROTEM samples. Two ROTEM samples will be drawn from each hypothermic trauma patient. The warmed 37°C sample will be compared to the sample analyzed at patients' core body temperature.

Secondary aims

Our secondary aim will be to evaluate if the coagulation parameter differences in hypothermic samples are replicated with TEG. Hypothermic TEG parameters will be compared against standard warmed TEG samples. Data for both TEG and ROTEM will be analyzed through our transfusion algorithm to determine if indicated blood products vary between hypothermic and warmed samples. We hypothesize that hypothermic TEG samples will demonstrate worse coagulopathy than warmed samples.

Tertiary aim

Determine if tranexamic acid (TXA) administration has an impact on fibrinolysis parameters in hypothermic patient samples. To assess TXA efficacy in hypothermic patients, a subset analysis in patients who receive TXA will be conducted. Hypothermic and standard assay results pertaining to fibrinolysis will be compared and will determine if a difference exists between samples.

Design

Prospective (observational with or without consent requirement)

Age: >18 years

Trauma patient

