Core body temperature below 35C

Inclusion Criteria

Requires ROTEM or TEG testing as part of workup

Patients taking anticoagulants will be included as part of this study

Patients who are normothermic or hyperthermic at time of admission

Known pre-existing coagulopathy

Exclusion Criteria

Patients less than 18 years of age

Pregnant patients

Please describe, completely but succinctly, how the project will be conducted.

The Principal Investigator will carefully monitor study procedures to protect the quality of the data and the integrity of the study. This will be a prospective multi-center observational study of trauma patients evaluated in the emergency department. Blood samples collected for routine ROTEM and TEG testing will use excess blood to run a secondary sample at the reported hypothermic patient temperature. To do this block (ROTEM) or cup (TEG) heaters will be used in the standard fashion for the 37° Celsius sample; the second block or cup will be analyzed at the patients core body temperature. In addition to general viscoelastic monitoring results, we will also be accessing patient records for information regarding injury pattern, clinical parameters on ED admission, comorbid medical conditions, treatment, and outcomes.

Primary Outcome

Primary outcome: Numeric difference in hypothermic vs. warmed ROTEM and TEG samples.

Secondary Outcome(s)

Secondary Outcome: Theoretical difference in indicated blood products based on hypothermic vs. warmed assay results for both TEG and ROTEM samples.

Select the variables to be collected & analyzed:

Baseline Participating Institution Information, Demographics, Baseline Clinical Characteristics, Hospital Course, Treatments & Interventions, Outcomes of Interest

Additional variables:

Full data collection below

All data collected will be stored in REDCap and de-identified prior to sharing with research team members or participating sites. REDCap-stored data will include and be categorized in the following manner: demographics, patient clinical background, pre-intake data, laboratory data, admission clinical or hemodynamic data, TEG- or ROTEM-indicated intervention, post-admission interventions used, and patient outcomes.

Demographics: age, gender, weight, height, ethnic group, race, blood type, anticoagulant usage

Transfer data as applicable: EMS/flight transfer time, blood product and pre-hospital interventions

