The primary effect of interest: Is there a statistical difference in coagulation metrics between hypothermic blood compared to warmed (current standard of care) blood in trauma patients? If so, what is the magnitude of difference between these testing methodologies?

The secondary effect of interest: Is there a statistical difference between hypothermic and standard viscoelastic tests that translates to clinically relevant changes regarding coagulopathy reversal? We plan to determine if using hypothermic TEG or ROTEM to guide resuscitation would result in a theoretically increased use of plasma, cryoprecipitate, platelets and TXA. To do this, we would determine the resuscitation strategy for each viscoelastic sample and – based on established transfusion thresholds – determine if hypothermic viscoelastic properties are different enough to result in a change in resuscitation approach (i.e., actual transfusion). Results of this study may inform future randomized controlled trials comparing the clinical effects of hypothermic patients treated with a resuscitation algorithm based on hypothermic ROTEM or TEG to those treated with standard ROTEM or TEG.

Include detailed description of the data analysis plan:

General Statistical Approach. Exploratory data analysis of all data collected will include the following overall summary measures for numerical variables: mean, standard deviation, minimum, maximum, and quartiles. For categorical data, we will construct frequency tables for each level within each variable. Bar charts, contingency tables, scatterplots and boxplots will be constructed to visualize associations as needed. Generalized linear models will be employed to evaluate relationships between variables, with random effect site (hospital), covariate effects for patient demographic and clinical characteristics, blood product and other intervention administration, TEG/ROTEM parameters by assay and temperature (hypothermic and warmed), and post-intervention clinical outcomes. Distributional, independence and homogeneity of variance assumptions will be investigated for each model evaluated and, if violated, transformations and/or nonparametric methods will be employed. Outliers will be identified

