In a pilot study, we found that hypothermic samples, as compared to warmed samples, yielded effect sizes (mean difference divided by standard deviation of differences) from 0.94 to 1.85 for ROTEM parameters A10, A20, alpha and MCF for both the intrinsic and extrinsic assays. For a sample size of 15 (paired) samples and Type I error rate of 0.05, an effect size of 0.8 will provide 82.1% power to detect a significant difference between the paired samples (2-sided test).

Include Power Analysis:

In the same pilot study, ROTEM-indicated standard of care intervention protocol was as follows: warmed – Plasma: 3/12 = 25%, Cryoprecipitate: 6/12 = 50%, Platelets: 0 / 12 = 0%; hypothermic – Plasma: 2/12 = 16.7%, Cryoprecipitate: 6/12 = 50%, Platelets: 3/12 = 25%. In all, 5/12 = 41.7% had a different ROTEM-derived treatment indication based on the warmed sample compared to the results from the hypothermic sample. Given a trauma patient from this population with an assumed probability of needing a blood product treatment of 0.25, collecting 50 paired samples will provide 81.1% power to detect a 20% difference in treatment indications for a 2-sided test given $\alpha = 0.05$, based on a normal approximation to a paired 2-sample proportion testing design. To replicate this in both ROTEM and TEG and account for incomplete data entries, we aim to collect 150 paired samples (75 ROTEM and 75 TEG) for the study. We believe this would be possible to obtain with 7-10 ROTEM and 7-10 TEG sites (14-20 sites total).

Please note what your enrollment procedure for this study entails:

To permit a consecutive sample of patients at clinical sites and avoid sampling bias, we request a waiver of consent to collect data via medical record review. This study is minimal risk, observational, and involves no additional interventional procedures. Laboratory specimens collected as part of this study will be obtained as routine standard of care with small aliquots of excess blood used for hypothermic testing. Additional vials of blood are not required to conduct this study. Hypothermic results will not be entered into the patient chart or used to direct patient care. Discussion and study buy-in with laboratory personnel will be required as part of this study. Enrolled patients will have a ROTEM or TEG performed according to standard site protocol, and then an additional sample run at their hypothermic temperature.

Outline consent procedures here, if applicable:

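### The primary aim is ROTEM only, but the primary outcome includes TEG and names no parameter, so the stated alpha and power cover one unspecified comparison

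*Protocol*

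**What the plan says.** The protocol ranks the TEG comparison in two different ways.

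- **Aims.** The hypothesis concerns ROTEM: "Our primary hypothesis is that results from hypothermic ROTEM assays will reflect more significant coagulopathy when compared to warmed samples". The primary aim follows it: "To test the primary hypothesis, hypothermic ROTEMs parameters will be compared against standard warmed ROTEM samples". TEG comes under Secondary aims: "Our secondary aim will be to evaluate if the coagulation parameter differences in hypothermic samples are replicated with TEG".
- **Primary Outcome.** Both devices appear together: "Primary outcome: Numeric difference in hypothermic vs. warmed ROTEM and TEG samples". No parameter, assay channel or summary measure is given.
- **Effects of Interest.** The primary question names no device and no direction: "Is there a statistical difference in coagulation metrics between hypothermic blood compared to warmed (current standard of care) blood in trauma patients". It goes on to ask how large the difference is.
- **Power Analysis.** The pilot effect sizes run "from 0.94 to 1.85 for ROTEM parameters A10, A20, alpha and MCF for both the intrinsic and extrinsic assays". The power claim reads "For a sample size of 15 (paired) samples and Type I error rate of 0.05, an effect size of 0.8 will provide 82.1% power", for a two-sided test. No TEG effect size is given. The planned total is 150 pairs, 75 per device.

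**The concern.** The same TEG comparison is secondary in the aims and primary in the outcome, and the Effects of Interest text does not settle which holds. The protocol's own literature review calls the hypothermic TEG data conflicting, so a clear ROTEM difference with little or no TEG difference is a realistic result. Under the aims, that would be a positive primary result that failed to replicate. Under the Primary Outcome text, it has no defined reading.

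Within ROTEM, the protocol lists several candidate parameters in two assay channels and ranks none of them first. It gives no rule for how many must differ, or which. The choice of primary comparison therefore stays open until the data are seen. The alpha and power are quoted for one comparison that is not identified. The results are meant to inform later randomized trials and possibly transfusion guidance, so it should be clear in advance which comparison carries the conclusion.

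**Working it through.** **1. Reproduce the stated power.** Inputs from the Power Analysis: n = 15 pairs, effect size d = 0.8 (mean difference over SD of differences), two-sided alpha 0.05. For a paired t-test, df = 14, the noncentrality is 0.8 × √15 = 3.098 and the critical value is 2.145. The noncentral t distribution gives a power of 82.13%, against 82.1% stated. A normal approximation (87.3%) and a one-sided t-test (90.3%) do not match. The 0.05 is therefore the error rate of one two-sided paired test, and the figure is right for that test.

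**2. Count the candidate comparisons.** The power basis has 4 parameters (A10, A20, alpha, MCF) × 2 channels = 8 ROTEM comparisons. The pilot summary also reports CFT in both channels, so the protocol mentions 10 in all. It names no TEG parameter as an endpoint. Eight for TEG is my assumption, made to match ROTEM.

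**3. Error rate if any one significant comparison answers the undirected question.** With k independent tests at 0.05, the chance of at least one false positive is 1 − 0.95^k:

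- k = 8: 1 − 0.95^8 = 33.7%
- k = 16: 1 − 0.95^16 = 56.0%

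Parameters read from one clot tracing are correlated, and the protocol gives no correlation, so a range is shown. Test statistics are taken as equally correlated normals within a device. The two devices are taken as independent, because separate ROTEM and TEG sites are planned.

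| Correlation within device | 8 ROTEM | 8 ROTEM + 8 TEG (assumed) |
|---|---|---|
| 0 | 34% | 56% |
| 0.5 | 25% | 44% |
| 0.8 | 16% | 29% |
| 0.9 | 12% | 22% |

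**4. If only the hypothesised direction counts.** Each test then contributes 0.025. With 8 independent tests, 1 − 0.975^8 = 18.3%. At correlations 0.5 and 0.8 the same model gives about 12.5% and 8%, roughly half the two-sided figures.

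**5. Cost of protection.** The same paired t formula with a Bonferroni split:

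| Alpha | Pairs | Effect size | Power |
|---|---|---|---|
| 0.05/8 | 15 | 0.8 | 48.2% |
| 0.05/8 | 24 | 0.8 | 80.6% |
| 0.05/10 | 50 | 0.8 | 99.6% |
| 0.05/10 | 75 | 0.5 | 92.0% |

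Fifteen pairs would not carry a split over eight comparisons. The planned 75 per device carry it easily. With one named primary comparison, the stated 82.1% at 15 pairs stands unchanged.

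**The case against.** Three stronger readings are tempting, and the protocol does not support them.

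- **That the stated 0.05 is wrong.** A reader might infer this from the number of parameters. The protocol attaches 0.05 to one paired comparison, where it is correct, and claims no control over a family of tests. A multiplicity procedure may also sit in a statistical analysis plan that is not at hand.
- **That the primary outcome is every ROTEM and TEG parameter, and that one significant result is success.** The text names no parameter and states no success rule. The primary effect of interest also asks for the size of the difference, which is estimation.
- **That the plan has a false-positive rate of 34% or 56%.** These figures hold only under that any-one rule, under independence and, for 56%, with an assumed TEG count. A directional reading roughly halves the ROTEM figures.

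It can also be said that no difference in any parameter is unlikely, given pilot effects of 0.94 to 1.85, and that the study is observational and changes no patient's care. Both points are fair and lower the urgency.

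They leave two things standing: the aims and the outcome disagree on whether TEG is primary, and no primary parameter is named. An analysis plan is the wrong place to settle which of two conflicting protocol statements governs.

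**Conclusion.** The point holds as an inconsistency and an unfixed primary endpoint, and should be fixed. The aims make ROTEM primary and TEG a replication, the Primary Outcome makes both primary, and neither names a parameter or channel. The 0.05 and the 82.1% are correct for one paired ROTEM comparison and do not extend to the primary question as a whole.

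The possible inflation is conditional. If any of the eight ROTEM comparisons could answer the undirected question, it is about 16% to 34% for correlations from 0.8 down to 0. With eight assumed TEG comparisons it is about 29% to 56%. The success rule, the correlations and the TEG count are assumptions. The contradiction between the sections does not depend on them.

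**What to change.** Reword the Primary Outcome to agree with the primary aim. Define it as the within-patient difference, core temperature minus 37°C, in one prespecified ROTEM parameter and assay channel. A short listed set of ROTEM parameters with an alpha split or a fixed testing order would serve equally well. Move TEG and the remaining ROTEM parameters to secondary outcomes, reported as mean differences with 95% confidence intervals. Bring the primary question under Effects of Interest into line, and say in the Power Analysis which comparison the 82.1% refers to.

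The cost is a protocol wording change made before the data are examined. Sample size and procedures stay as they are. Even a split over all ten ROTEM comparisons that the protocol mentions leaves the power shown above at 50 to 75 pairs.

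### The one stated model has site as its only random effect and no within-patient term, so it does not match the paired basis of both power statements

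*Protocol*

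**What the plan says.** **Design.** Under the primary aim, "Two ROTEM samples will be drawn from each hypothermic trauma patient", one analysed at 37°C and one at core temperature. The outcome field reads: "Primary outcome: Numeric difference in hypothermic vs. warmed ROTEM and TEG samples".

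**Analysis.** Under General Statistical Approach, in the data analysis plan, one model is stated: "Generalized linear models will be employed to evaluate relationships between variables, with random effect site (hospital". The same sentence lists covariate effects and "TEG/ROTEM parameters by assay and temperature (hypothermic and warmed". No patient effect, repeated-measures term, paired t-test or McNemar test is named. Then: "Distributional, independence and homogeneity of variance assumptions will be investigated for each model evaluated", with transformation or a nonparametric method as the fallback.

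**Power.** The Power Analysis section reports pilot "effect sizes (mean difference divided by standard deviation of differences) from 0.94 to 1.85" and then: "For a sample size of 15 (paired) samples and Type I error rate of 0.05, an effect size of 0.8 will provide 82.1% power". The product-indication calculation (50 pairs, 20% difference, 81.1%) is also described as a paired comparison of proportions. The target is 75 ROTEM and 75 TEG pairs, from 7–10 sites for each device.

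**The concern.** The strongest dependence in these data is between the two results from one patient. The plan does fix a random-effects structure, but at hospital level only. With 75 pairs over 7–10 sites there are about 7.5 to 10.7 patients per site, so a site intercept cannot stand in for a patient intercept. Patient covariates explain only part of the between-patient variation.

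If the model is fitted to one row per sample, between-patient variation stays in the residual against which temperature is tested, although it cancels in the within-patient difference. The protocol asks for the magnitude of the temperature effect as well as its significance, so wrong standard errors matter even where power is ample.

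The fallback does not repair this. Independence fails by design, a transformation does not restore pairing, and a nonparametric test does so only if it is a paired one, which is not stated.

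**Working it through.** **Inputs.** From the Power Analysis section: 15 pairs, two-sided α 0.05, effect size dz = 0.8 (mean difference over SD of differences), 75 pairs planned per device; for indications, 50 pairs, reference rate 0.25, difference 0.20, power 81.1%. The correlation ρ (after site and covariates) and the discordance are not given, so both are assumptions.

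**1. The plan's own figure.** Paired t-test with 14 df and noncentrality 0.8 × √15 = 3.098: power 82.13%, matching 82.1%. A plain normal approximation gives 87.3%. The figure rests on a paired t-test.

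**2. Standard error without a patient term.** With SD σ for a single reading, the mean difference has true standard error σ√(2(1−ρ)/n). Treating the samples as independent gives σ√(2/n). The ratio is 1/√(1−ρ): 1.41 at ρ = 0.5, 2.24 at 0.8, 3.16 at 0.9.

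**3. Power of the unpaired test on correlated pairs.** To a first approximation, power = Φ(dz√n − 1.96/√(1−ρ)). For n = 75, dz = 0.8, ρ = 0.9: 0.8 × 8.660 = 6.928; 1.96/0.3162 = 6.198; Φ(0.730) = 77%. Simulation, using t critical values and the sampling variation of the pooled SD, gives:

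| Case | Paired | ρ = 0.5 | ρ = 0.8 | ρ = 0.9 |
|---|---|---|---|---|
| 15 pairs, dz 0.8 | 82% | 59% | 13% | 1% |
| 75 pairs, dz 0.8 | >99.9% | >99.9% | 99% | 74% |
| 75 pairs, dz 0.4 | 93% | 75% | about 18% | 0.6% |

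The usual two-sample power formula would not serve here, because it assumes that the data really are independent. The dz 0.4 row is illustrative: it is half the planning value and below the pilot range.

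**4. Type I error.** At 75 pairs, the nominal 5% becomes about 2% at ρ = 0.3, 0.6% at 0.5 and below 0.1% at 0.7. The error is conservative.

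**5. Is a high ρ plausible?** The pilot reports a mean EXTEM MCF fall of 3.0 mm. With dz between 0.94 and 1.85, the SD of differences is between 3.0/1.85 = 1.62 and 3.0/0.94 = 3.19 mm. Since ρ = 1 − SD_diff²/(2σ²), ρ reaches 0.8 when σ is 2.6–5.0 mm (SD_diff/√0.4) and 0.9 when σ is 3.6–7.1 mm (SD_diff/√0.2). The protocol does not give σ.

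**6. Product indications.** Assume rates 0.25 and 0.45 with total discordance 0.26. The McNemar normal approximation at 50 pairs is Φ[(0.20√50 − 1.96√0.26)/√(0.26 − 0.04)] = Φ(0.884) = 81.2%, close to the stated 81.1%.

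- Unpaired test on those pairs: critical difference 1.96 × √(2 × 0.35 × 0.65/50) = 0.187; true standard error √(0.22/50) = 0.0663; Φ((0.20 − 0.187)/0.0663) = 58%.
- Two truly independent groups of 50: 55.6%.
- At 75 complete pairs, the same formulas give 94% paired and 81% unpaired.

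The 81.1% is not uniquely recoverable. A one-sample form with variance 0.45 × 0.55 also gives 81.1%. An independent comparison of 0.25 with 0.05 gives 80.9%; in that direction, losing the pairing costs little at this discordance.

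**The case against.** The strongest reply is that the text is general, not wrong. It speaks of relationships between variables and defines neither a response nor a row structure. The primary outcome is a numeric difference. If that difference is computed per patient and used as the response, a random site effect is enough and the pairing is kept. The power section plainly intends paired tests, independence is to be checked, the available analysis text breaks off mid-sentence after the model statement, and an analysis plan not shown may settle the matter.

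Much of this stands, and it rules out three stronger readings that a reader might infer.

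- **That the plan definitely treats the two samples as independent.** The difference-score reading is open, so this is not established.
- **That the stated power will not be delivered.** At 75 pairs and dz 0.8, the primary comparison keeps about 99% power up to ρ = 0.8. At dz 0.94, the bottom of the pilot range, it is still 96% at ρ = 0.9. Nor can the error create a false positive.
- **That post-intervention outcomes are to be covariates in the temperature contrast.** The list serves models in general and itself includes the TEG/ROTEM parameters, so it cannot be the covariate set of a model whose response is those parameters.

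The mismatch itself remains. The model sentence is complete, names one random effect at the wrong level for this contrast, and lists results by temperature, which suggests one row per sample. An analysis plan that followed it literally would inherit the fault. The independence check leads to no remedy that is said to be paired.

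**Conclusion.** Wrong as written, in a limited sense: the stated model names no patient-level term and does not say that it is fitted to within-patient differences, whereas both power statements are paired. That mismatch needs no assumption.

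The size does, and it applies only if the model is fitted to one row per sample. Standard errors are then 1.4 to 3.2 times too large for ρ from 0.5 to 0.9, and tests are conservative. At the 15-pair planning case the power loss is severe; at the planned 75 pairs and dz 0.8 it is small unless ρ is about 0.9. The main cost is over-wide intervals around the temperature effect, and a fall to about 56–58% at 50 pairs for product indications under the assumed rates and discordance. Smaller analyses, such as the TXA subset, are more exposed than the full sample.

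**What to change.** In General Statistical Approach, state that:

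- the primary analysis models the per-patient difference (hypothermic minus 37°C) with a random site intercept, or uses a mixed model with patient nested in site and temperature as a within-patient factor;
- product indications are compared by McNemar's test, or by a conditional or patient-random-effect logistic model;
- any nonparametric fallback for the temperature contrast is a paired one, such as the Wilcoxon signed-rank test.

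The cost is one or two sentences of analysis wording. Enrolment, data collection and the stated sample size do not change.
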